7.5.5 Pregnancies

A detailed listing of all pregnancies will be provided.

7.5.6 Eastern Cooperative Oncology Group (ECOG) Performance Scores

Number of percent of subjects for each category of the ECOG performance status at each assessment time will be provided by treatment group. Negative change scores indicate an improvement and positive scores indicate a decline in performance.

7.5.7 Ophthalmologic Assessment

Quantitative ophthalmologic variable (logmar score for visual acuity) will be summarized using mean, standard deviation, minimum, maximum and median by treatment group at each visit for each eye.

7.6 Analysis of PK

PK analysis will be conducted on the PKAS.

Plasma concentrations of ASP2215 will be summarized by treatment group and where appropriate by nominal time points using descriptive statistics, including number of subjects,

mean, standard deviation, minimum, median, maximum, geometric mean, and coefficient of variation (CV).

Population pharmacokinetic analysis will be performed. Data from this study may be pooled with other studies for analysis. Details of this analysis will be specified in a separate population pharmacokinetic analysis plan.

7.7 Analysis of PD

Not applicable.

7.8 Subgroups of Interest

There will be no efficacy analysis and subgroup analysis performed for the end of study report.

Co-primary efficacy endpoints (OS and CR/CRh rate) and key secondary endpoints (EFS and CR rate) will be summarized by treatment groups at the appropriate interim/final analysis timing for the subgroups defined on the basis of the categorized variables listed below:

Sponsor: Astellas Pharma Global Development, Inc.

ISN/Protocol 2215-CL-0301

Grouping variable Subgroups
Age group < 65 years

>=65 years

Sex Female

Male

Race White

Black or African American

Asian Other

Baseline ECOG 0-1

>=2

Region North America

Europe (including Turkey and Israel)

Asia

Central FLT3 Mutation Type FLT3-ITD alone

FLT3-TKD alone FLT3-ITD & TKD

Others (Unknown/Missing/Negative)

Response to First-line Therapy Relapse within 6 months after allogeneic HSCT

Relapse after 6 months after allogeneic HSCT

Primary refractory without HSCT

Relapse within 6 months after CRc and no HSCT Relapse after 6 months after CRc and no HSCT

Salvage Chemotherapy High intensity chemotherapy (FLAG-IDA, MEC)

Low intensity chemotherapy (LoDAC or azacitidine)

Prior Use of FLT3 inhibitor Yes

No

Cytogenetic Risk Status Favorable

Intermediate Unfavorable

Other

Pooled stratification factors, if used for stratified analysis, will also be included in subgroup analysis.

7.9 Other Analyses

7.9.1 PK-PD Analysis

There will be no exploratory PKPD analysis performed for the end of study report.

Exploratory PKPD analysis will be performed on safety and efficacy variables. Graphical approaches will be performed on selected variables. Modeling (including mixed effect modeling) may be performed if warranted.

7.10 Interim Analysis (and Early Discontinuation of the Clinical Study)

To evaluate whether ASP2215 is particularly beneficial or harmful compared to the benchmark data or the salvage chemotherapy group while the study is ongoing, two interim analyses are planned. At the interim analyses, production of tables and listings will be performed by an independent data analysis center (IDAC). The interim analysis outputs will be reviewed by IDMC. No member of the clinical study team will have access to the tables and listings created for the IDMC. For more details consult the IDMC Charter.

First Interim Analysis

The first interim analysis is planned when approximately 141 subjects are randomized into ASP2215 arm and at least 112 days (4 treatment cycles) post first dose or randomization (for subjects who received no study drug. At the first interim analysis, only the co-primary endpoint of CR/CRh rate will be evaluated for subjects in ASP2215 arm. The two-sided 95% exact confidence interval of CR/CRh rate will be calculated for approximately 141 subjects who are randomized into ASP2215 arm and at least 112 days (4 treatment cycles) post first dose or randomization (for subjects who received no study drug), i.e., ASP2215 group in RAS. The IDMC will inform Sponsor the outcome on CR/CRh endpoint as favorable or unfavorable at the first interim analysis, using the decision rules specified in table below:

Decision Rules based on lower limit of two-sided 95% exact confidence interval of CR/CRh rate in ASP2215 arm at First Interim Analysis

CR/CRh Rate with two-sided 95% exact confidence interval			
Lower limit <=12% Lower limit > 12%			
Unfavorable	Favorable		

The Sponsor may prepare a regulatory submission for conditional approval using the first interim analysis data. However, the study conduct will not be impacted by the first interim analysis result.

A nominal 1-sided p-value 0.0005 (i.e., 2-sided p-value 0.001) which is arbitrarily selected, will be spent to acknowledge the single-arm CR/CRh rate evaluation at the first interim analysis and will not be recycled in the second interim analysis and final analysis. No formal hypothesis testing will be conducted for CR/CRh rate for the study, only the descriptive statistics including two-sided 95% exact CI of CR/CRh rate will be provided to IDMC at the first interim. The hypothesis testing for the primary and secondary endpoints of OS, EFS and CR rate at the secondary interim analysis and final analysis are well controlled at an overall 1-sided type I error rate 0.0245 based on a sequential testing procedure.

Second Interim Analysis

The second interim analysis will be performed when approximately 50% of the total planned death events (death event = 129) have occurred for the study. OS will be tested at 1-sided 0.00147/0.38674 significant level for efficacy/futility according to the O'Brien-Fleming type alpha/beta spending function. The IDMC may recommend terminating the trial for favorable or unfavorable results at the second interim analysis based on OS endpoint, using the decision rules specified in table below:

Decision Rules based on 1-sided P-Value obtained at Second Interim Analysis

Overall Survival				
P-value ≥ 0.38674 0.38674>P-value ≥ 0.00147 P-value < 0.00147				
Unfavorable: Trial may be stopped for Futility	Trial continues	Favorable: Trial may be stopped for Efficacy		

The futility bound of this study is non-binding and is considered guidance rather than strict bound. Depending on the recommendations of the IDMC, the Sponsor may prepare a regulatory submission, if the outcome on OS at the second interim analysis is favorable.

If the study is not stopped after the second interim analysis, a final analysis based on OS will occur after 100% of the total planned death events (death events = 258) have been observed. The 1-sided significance level for the final analysis is 0.02402 for OS.

According to the sequential testing procedure on controlling overall type I error rate for multiple endpoints, EFS will be tested when the null hypothesis of OS is rejected at the second interim or at the final analyses. CR rate will be tested when the null hypotheses of both OS and EFS are rejected hierarchically at the second interim or at the final analyses. Their significance levels at the second interim and final analyses will be based on Pocock/O'Brien-Fleming alpha/beta spending function. The details about the significance levels at each interim and final analyses for each co-primary and secondary endpoints are specified in Section 7.4 Table 4.

Details for the two formal interim analyses and the IDMC safety review procedures will be included in either Interim Analysis Plan (IAP) or IDMC Charter. The statistical analysis plan for the interim analyses will be described in interim analysis plan (IAP). Safety data including AE, lab, vital signs and ECG will be reviewed by IDMC on a periodic basis. The procedures for IDMC safety review will be described in the IDMC charter.

7.11 Handling of Missing Data, Outliers, Visit Windows, and Other Information

7.11.1 Missing Data

Every effort will be made to resolve incomplete dates for death and disease relapse. If a partial date cannot be resolved, the most conservative imputation methods will be used to complete the missing information.

For primary endpoint OS, missing or incomplete death date will be imputed as the earliest feasible date on or after the date of last contact as the examples shown in the table below. The date of last contact will be obtained as described in Section 6.1.1.

Incomplete Date of Death (YYYY MMM DD)	Date of Last Contact (YYYY MMM DD)	Imputed Date of Death (YYYY MMM DD)
2005 APR ??	2005 MAR 31	2005 APR 01
2005 ??? 13	2005 MAR 31	2005 APR 13
2005 ??? ??	2005 MAR 31	2005 MAR 31
???? APR ??	2005 MAR 31	2005 APR 01
???? APR 13	2005 MAR 31	2005 APR 13
???? ??? ??	2005 MAR 31	2005 MAR 31

Partial relapse dates will be imputed to the first day of the month of the missing parameter but not earlier than the last disease assessment date. A month and year must be present or the date will remain missing.

Missing centrally evaluated bone marrow assessment will be imputed with local bone marrow assessment as described in Section 6.1.3.3. Non-responder imputation will be used for binary response variables.

Missing or partial start and stop dates of adverse events and concomitant medication will be imputed using the following algorithm:

- Imputation rules for partial or missing stop dates:
 - o If the month and year are present, then impute as the last day of that month.
 - o If only the year is present, impute as December 31 of that year.
 - o If the stop date is entirely missing, assume the event or medication is ongoing.
- Imputation rules for partial or missing start dates:

		Stop Date						
		Complete: yyyymmdd		Partial: yyyymm		Partial: yyyy		missing
				< 1 st		< 1 st	$\geq 1^{st}$	
			$\geq 1^{st}$	dose	$\geq 1^{st}$ dose	dose	dose	
Sta	rt Date	< 1st dose	dose	yyyymm	yyyymm	уууу	уууу	
Partial:	= 1 st dose yyyymm	2	1	n/a	1	n/a	1	1
уууутт	≠ 1 st dose yyyymm	2	2	2	2	2	2	2
Partial:	= 1st dose $yyyy$	3	1		1	n/a	1	1
уууу	$\neq 1^{st}$ dose $yyyy$	3	3	3	3	3	3	3
M	issing	4	1	4	1	4	1	1

^{1 =} Impute as the date of first dose; 2 = Impute as the first of the month; 3 = Impute as January 1 of the year; 4 = Impute as January 1 of the stop year

The imputed dates will be used to determine whether an AE is/is not treatment emergent. Listings of AEs and concomitant medications will present the actual partial dates; imputed dates will not be shown.

In the case of partial date of initial diagnosis of AML, the date will be imputed to the first day of the month. A month and year must be present or the date will remain missing.

In the case of partial starting date of subsequent AML therapy, the date will be imputed to the first day of the month but not earlier than the last dosing date of the study drug. A month and year must be present or the date will remain missing.

Concentrations below the lower limit of quantification (BQL) in PK should be treated as missing when the terminal elimination rate constant is evaluated. Otherwise BQL should be treated as zero in the estimation of individual pharmacokinetic parameters.

7.11.2 Outliers

All values will be included in the analyses.

7.11.3 Visit Windows

Visit windows are allowed for certain visits per the schedule of assessments. Subject data will not be excluded from analyses due to the subject's failure to comply with the visit schedule. CRF visit will be used for analysis. In the case of multiple observations at a specific visit, the observation which is closest to the target date will be used. If the observations have the same distance to the target visit, the latest one will be used. If more than one observation is made on the same day, an average value if continuous or the worst value if categorical will be included in the analysis.

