- c. Includes medications taken within 28 days prior to cycle 1 day 1.
- d. Woman of childbearing potential must have a negative serum or urine pregnancy test (minimum sensitivity 25 IU/L or equivalent units of human chorionic gonadotropin) within 72 hours prior to the start of study treatment.
- e. Screening ECG is required. ECG assessment will be evaluated at predose of cycle 1 day 1, cycle 1 day 8, cycle 1 day 15 and day 1 of each subsequent cycle. Predose assessments should be taken within 1 hour before drug administration. The 12-lead ECGs will be recorded in triplicate (3 separate ECGs 10 minutes resting prior to first ECG and at least 5 minutes apart per time point) and transmitted electronically for central reading. The mean QTcF of the triplicate ECG tracings based on central reading will be used for final treatment decisions and AE reporting. If the mean of the triplicate QTcF is > 500 ms at any time point (by either value on ECG tracing printout or central reading), then triplicate ECGs will be repeated (within 2 hours if based on value on ECG tracing printout and as soon as possible if based on central reading). If the repeat ECG confirms a mean of the triplicate QTcF > 500 ms, dosing of ASP2215 will be interrupted for up to 14 days. While ASP2215 may be interrupted temporarily based on value on ECG tracing printout, the central reading should be used for final treatment decisions. Cardiology consult will be obtained as medically indicated. If QTcF resolves to ≤ 480 ms (grade 1 or less) by central reading within 14 days, the subject may resume dosing at the reduced dose.
- f. Urinalysis only required at screening. Uric acid will be tested on days 1, 4, 8 and 15 in cycle 1. Additional laboratory tests should be performed according to institutional standard of care.
- g. Subjects may be screened and randomized from local labs only. However, samples must also be submitted for central read. Labs and/or ECG can be repeated during screening period.
- h. MUGA scans or ECHO (per standard of care) are to be performed at screening for subjects with history of congestive heart failure New York Heart Association Class 3 or 4 (unless MUGA scans or ECHO performed either within 1 month prior revealed left ventricular ejection fraction ≥ 45%).

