- q. Includes Brief Fatigue Inventory, Functional Assessment of Chronic Illness Therapy–Dyspnea-Short Forms, Functional Assessment of Cancer Therapy-Leukemia and dizziness and mouth sores items. The BFI will be administered at cycle 1 day 1 predose, cycle 1 day 8 (± 1 day), day 15(± 1 day), cycle 2 day 1 (± 2 days), day 15(± 1 day) and all subsequent cycles day 1 (± 2 days). Functional Assessment of Chronic Illness Therapy–Dyspnea-Short Forms, Functional Assessment of Cancer Therapy-Leukemia and dizziness and mouth sores items will be administered at cycle 1 day 1 predose, cycle 2 day 1 (± 2 days) and all subsequent cycles day 1 (± 2 days).
- r. If possible, patient reported outcome measures should be performed prior to any other assessments on that visit day.
- s. A cycle 1 day 8 ECG will be taken and the central read results will be provided to the site 24 hours after receipt of the tracing. A confirmatory ECG should be performed on cycle 1 day 9 if the mean QTcF from cycle 1 day 1 to cycle 1 day 8 has increased > 30 ms with no other known etiology, based on the central read ECG. On cycle 1 day 8, it is recommended that the ECG is taken as early as possible in the morning and transmitted immediately. In addition, it is recommended that the cycle 1 day 9 visit is scheduled later in the day in order to allow for receipt and assessment of the cycle 1 day 8 central read ECG. This also allows for a subject to be contacted if the cycle 1 day 9 ECG is no longer required. If the cycle 1 day 9 ECG is still required, the result of the central read ECG will be received on cycle 1 day 10, in which the investigator should assess if the ASP2215 dose modification should occur as per the dose interruption or reduction guideline in Section 5.1.2 of the protocol.
- t. Thyroid function tests will be repeated after every 2 cycles of therapy (C3D1, C5D1, C7D1, etc.).

Table 2 Schedule of Assessments for Chemotherapy Arm

	Screening		Cv	cle 1		Cvo	ele 2	Subsequent Cycles
Activity	(Day -14		Day 4	Day 8	Day 15	Day 1	Day 15	Day 1
	to -1)	Day 1	± 1	± 1	± 1	± 2	± 1	± 2
Signed ICF	X							
Medical and Disease History	X							
Randomization		X^p						
Physical Examination ^b	X	Xa	X	X	X	X	X	X
Vital Signs	X	Xa	X	X	X	X	X	X
ECOG Performance	X	Xa			X	X	X	X
Prior and Concomitant Medications	X ^c	X	X	X	X	X	X	X
Pregnancy Test for Woman of Childbearing Potential	X ^d	X				X		X
Chest X-ray (or CT of chest) ^o	X							
12-lead ECG ^e	Xg	X			X	X		X

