7.5.4 Electrocardiograms (ECGs)

12-lead ECGs will be recorded in triplicate at the scheduled time points. Each ECG tracing will be taken 5 minutes apart. ECGs will be read at the site for clinical decision making and transmitted to a central reviewer. Data from the central reviewer will be used in summary presentations. The three values of each ECG parameter within a time point from the central reviewer will be averaged to determine time-specific parameter for a subject, and used in summaries.

The QT interval corrected for heart rate by Fridericia's formula, QTcF, is defined as: $QTc(F) = QT/(RR)^{0.33}$, where RR interval is inversely proportional to heart rate (approximately RR = 60/heart rate).

The QTcF interval will be summarized using frequency tables for each treatment group at each treatment visit and time point for values of clinical importance using the range criteria below.

	QTc Interval Criteria Value (msec)	
	Interval Category	
Normal	≤ 450	
Borderline	$> 450 \text{ to } \le 480$	
Prolonged	$> 480 \text{ to} \le 500$	
Clinically significant	> 500	

Number and percent of subjects with maximum postbaseline QTcF > 480 msec and the time to maximum post baseline QTcF value > 480 msec will be summarized by treatment group.

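### The generic visit rules in SAP 7.11.3 can average away or drop an unconfirmed central QTcF above 500 ms in the only QTcF table that counts that category

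*SAP*

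**What the plan says.** **Repeat ECGs.** SAP Section 2, Schedule of Assessments for ASP2215 Arm, footnote e sets the trigger: "If the mean of the triplicate QTcF is > 500 ms at any time point (by either value on ECG tracing printout or central reading". It continues: "then triplicate ECGs will be repeated (within 2 hours if based on value on ECG tracing printout". If the trigger is the central reading, the repeat is to follow as soon as possible. The next step depends on confirmation: "If the repeat ECG confirms a mean of the triplicate QTcF > 500 ms".

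**Several observations at one visit.** Section 7.11.3 analyses by CRF visit. For observations on different days: "In the case of multiple observations at a specific visit, the observation which is closest to the target date will be used". A tie in distance goes to the later one. For the same day: "If more than one observation is made on the same day, an average value if continuous or the worst value if categorical will be included". Neither rule excepts ECGs.

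**QTcF outputs.** Section 7.5.4 averages the three central values within a time point. It then tabulates QTcF by visit and time point in four categories: up to 450, above 450 to 480, above 480 to 500, and above 500 ms, the last labelled clinically significant. It also plans a subject-level summary: "Number and percent of subjects with maximum postbaseline QTcF > 480 msec and the time to maximum post baseline QTcF value > 480 msec". It does not say how a repeat triplicate enters either output.

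**The concern.** Averaging the three tracings of one triplicate is sound. A second triplicate taken because the first was extreme is a different matter, since the repeat depends on the value it is then averaged with. If the first triplicate is above 500 ms and the repeat is lower, the pooled value can fall into the 480-500 row although the central reader measured more than 500 ms.

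The category concerned is the plan's own highest one. The maximum-based summary stops at 480 ms, so the by-visit table is the only output in 7.5.4 that counts values above 500 ms. For liver tests (7.5.2.1) and vital signs (7.5.3), the plan states that each subject's highest value is used for the thresholds. No such statement covers QTcF above 500 ms. Version 4.0 of the SAP governs an end-of-study analysis of safety data only, so the rule bears on the outputs this version is written for.

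**Working it through.** The plan states no figure on this point, so there is none to reproduce. The check has four steps.

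**1. Which rule applies.** A repeat within 2 hours of a printout trigger is in effect on the same day, so the averaging rule reaches it. For a central trigger, the only stated turnaround concerns cycle 1 day 8: "the central read results will be provided to the site 24 hours after receipt of the tracing". Such a repeat would normally fall on a later day, where the closest-to-target rule applies if both ECGs sit under one CRF visit. The documents do not give the split between the two kinds of trigger.

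**2. Same-day arithmetic.** Let T1 > 500 be the first central triplicate mean and T2 the repeat. Then (T1 + T2)/2 ≤ 500 if and only if T2 ≤ 1000 − T1.

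| T1 (ms) | Average is 500 or less if T2 is at most | Average is 480 or less if T2 is at most |
|---|---|---|
| 505 | 495 | 455 |
| 510 | 490 | 450 |
| 520 | 480 | 440 |

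Example: T1 = 506 and T2 = 492 give (506 + 492)/2 = 499, tabulated in the 480-500 row. If T1 and T2 both exceed 500, the average exceeds 500, so a confirmed crossing always stays.

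**3. Other-day case.** Take a visit with a window of ± 2 days, a trigger one day before target and a repeat on the target day. Only the repeat is kept and the trigger is dropped, whatever its size. With the trigger on the target day and the repeat a day later, the trigger is kept. If both exceed 500 ms, the one retained also does.

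**4. Size of the same-day effect.** This needs variability figures that the documents do not give, so the following are assumptions. Underlying QTcF is normal, each triplicate mean has independent normal error, and the repeat is made only if the first central mean exceeds 500 ms.

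| Mean (ms) | Between-subject SD (ms) | SD of a triplicate mean (ms) | Share of triggered visits with average 500 or less |
|---|---|---|---|
| 430-450 | 25 | 6 | 18-25% |
| 430-450 | 25 | 8 | 24-33% |
| 430-450 | 25 | 10 | 30-41% |
| 440-450 | 20 | 5 | 23-28% |
| 440-450 | 20 | 8 | 37-43% |
| 440-450 | 20 | 12 | 50-58% |

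In the settings with SD 20:

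- Among crossings confirmed by the repeat, 0% were lost.
- Among visits with underlying QTcF above 500 ms, about 6% to 12% were lost.
- Of the averages at 500 ms or below, about 84% to 97% came from visits with underlying QTcF of 500 ms or less.
- The average fell to 480 ms or below in 0% to 2.2% of triggered visits.

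At a fixed underlying value, with the same error SDs (5, 8 and 12 ms), the loss was 13-19% at 502 ms, 3-12% at 505 ms and 0.1-5% at 510 ms.

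**The case against.** The strongest reply is that 7.5.4 is the specific ECG rule. It averages only the three values within a time point, so a repeat could count as its own time point or sit under an unscheduled CRF visit that 7.11.3 does not reach. The output is also a frequency table, so the worst-value branch for categorical data could apply and would keep the crossing. These readings are open, but the plan chooses none of them. QTcF in ms is continuous and only its display is categorised, so the literal reading is the averaging one. Two programmers could follow the text and report different counts above 500 ms.

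Three stronger readings are tempting, and the SAP does not support them.

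- **True crossings are systematically lost.** A reader might infer this. But a crossing confirmed by the repeat, which is the plan's own test, cannot be averaged away, and most of those that move are probably measurement noise.
- **The rule acts only on high values and only downwards.** The printout can trigger a repeat while only central readings are tabulated. A central 497 followed by 512 averages 504.5 and moves up a category. Screening ECGs may be repeated without this trigger, and footnote s calls for a cycle 1 day 9 ECG after a rise above 30 ms.
- **Only the ASP2215 arm is affected.** The chemotherapy schedule states no repeat rule, but its ECG footnote refers to a protocol section that is not at hand.

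It is also true that footnote e bases final treatment decisions and AE reporting on the central triplicate mean, and that QT prolongation is analysed separately as an adverse event of interest. Neither route depends on 7.11.3, so the consequence is confined to a descriptive table.

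**Conclusion.** The point holds in a limited form. Read literally, 7.11.3 averages a triggered same-day repeat with its trigger and can discard the trigger when the repeat falls on another day. An unconfirmed central QTcF above 500 ms can then be missing from the above-500 row of the by-visit table, the only place in 7.5.4 where it would be counted. Across the assumptions tried, about 18% to 58% of same-day triggered visits would move. That range rests wholly on assumed means and SDs, and applies only where the first central reading itself exceeds 500 ms and the repeat is on the same day under the same visit. The documents do not allow a count of affected subjects. The maximum-based summary at 480 ms is barely affected. A change is still warranted because this is a stated rule rather than a mere silence, and it blends or drops safety values whose repeat exists because the first reading was extreme.

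**What to change.** - **7.5.4:** state that averaging is limited to the three central tracings of one triplicate, and that a repeat triplicate is a separate observation.
- **7.11.3:** exempt QTcF from same-day averaging and from closest-to-target selection in threshold summaries.
- **7.5.4:** derive the maximum post-baseline QTcF from all central triplicates, including repeat and unscheduled ones. Add a count above 500 ms beside the one above 480 ms.
- **7.5.4:** show confirmed values above 500 ms in a separate row.

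The cost is SAP wording and minor reprogramming of one derivation. The count above 500 ms may rise slightly and will include unconfirmed readings, which the separate row makes visible. Trial conduct and clinical rules are unchanged.
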